PROTOCOL SYNOPSIS

Sponsor / Sponsor-Investigator	Centre Hospitalier Universitaire Vaudois (CHUV), Lausanne, Switzerland
Study Title:	Prediction of massive transfusion in trauma patients in prehospital and in-hospital: Data from Swiss Trauma Registry (STR)
Acronym:	Massive transfusion Prediction Study (MTP Study)
Protocol Version and Date:	Version n°1, 11.09.2020
Trial registration:	Swiss trauma Registry: NCT0352602 MTP study: pending
Study category and Rationale	Our study is an observational non-interventional study based on a multicentric swiss register (Swiss trauma Registry) based on retrospective anonymized data.
Clinical Phase:	No Clinical phase: Observational study

Background and Rationale:
	
Since the 2000s, many prognostic scores were developed to predict traumatic haemorrhage. Most of these studies were retrospectives based on registers. Due to missing data of death due to bleeding, these studies chose to predict the risk of massive transfusion as a surrogate of haemorrhagic death. These scores include clinical parameters (Vital signs), laboratory values (haemoglobin, lactate, Base excess) and/or imaging (CT or ultrasound) values. The scores showing best performance are the Trauma Associated Severe Hemorrhage (TASH) score, developed and validated on the German register (DGU-Register) (1, 2) and the ABC score developed and validated in the United States of America (3, 4).
 
However, the majority of these scores cannot be applied at the scene of the injury due to the unavailability of laboratory and imaging values. Therefore, their clinical utility remains unclear. To overcome the need of diagnostic tests, authors have developed and recently validated a clinical prognostic score in identifying trauma patients with or at risk of significant haemorrhage based on predicted probabilities of death due to bleeding: BATT score (5). This score was developed from an international cohort using data from 271 Trauma Centres in 41 countries on 5 continents and uses first clinical parameters at initial assessment. The BATT score predicts death due to bleeding and has been validated on a large population in England and Wales. It could also predict massive transfusion, as a surrogate of haemorrhagic death, earlier at the scene of injury. Its feasibility and external validation would make its clinical utility superior to other scores while identifying a greater number of patients requiring early management.


Objective(s):
	
 - External validation of pre-existing prognostic scores of traumatic haemorrhages at different times of care (Scene of Injury, admission at the trauma room) in order to assess their overall performance, discrimination and calibration in the prediction of massive transfusion and haemorrhagic death. - Comparison of score performances (Overall performance, discrimination and calibration).

Outcome(s):
	
Primary study outcome :
 
 - Massive transfusion defined by a transfusion equal to or greater than 10 Red blood cell (RBC) / 24 hours or ≥ 3 RBC in the first hour if available in the Swiss Trauma Registry. 
Secondary study outcome :
 
 - Death due to bleeding (if available in the registry) - Early death (< 24 hours) - Coagulopathy at admission defined by INR > 1.2, quick TP < 70% or Fibrinogen < 1.5 g/L (6,7,8)

Study design:
	
Observational non-interventional study based on a multicentric anonymized registry

Inclusion / Exclusion criteria:	
Study population: All adult trauma patients treated at twelve Swiss trauma centres Level I from 01.01.2015 to 31.12.2019 with eligible criteria of the Swiss Trauma Registry (STR) are included. All data from the register are anonymised without any access to medical files. The identity of the trauma patients, date of birth, address and trauma scene location are unknown (as mandatory by the swiss law: Art. 2 ORH).
 
Inclusion criteria:
 
- Age > 16 years old- ISS (Injury Severity Score) ≥ 16 and/or AIS head (Abbreviated Injured scale) ≥ 3 
Exclusion criteria:
 
- Age < 16 years old- ISS < 16 and or AIS < 3- Isolated Burns (including electric shock) or if the burn is clearly the primary injury- Patients arriving at the trauma room with no sign of life and no diagnostic/therapeutic measures have been initiated for them- Choking or hanging patient without any other injury.- Drowning patients
--	---


Measurements and procedures:
	
Predictive Variables:
 
Demographics: Age, gender, type of accident, mechanism of Injury (penetrating/blunt), Hospital (anonymised by number), Date and time of accident.
 
Prehospital settings: Arrival on scene (paramedics, date/time and medics, date/time), type of transport: physician staffed ambulance/helicopter, Firsts clinical measures recorded: Systolic blood pressure (SBP), Respiratory rate (RR), Heart Rate (HR), Pulse Oximetry, Glasgow coma scale, temperature, cardiopulmonary reanimation, Drugs Use: Tranexamic acid (Date/time) and vasoactive, early death before arriving to the hospital.
 
In-hospital settings (trauma room): Hospital arrival (date/hour), Firsts measures: Systolic blood pressure (SBP), Respiratory rate (RR), Heart Rate (HR), Pulse Oximetry, Glasgow coma scale, temperature, cardiopulmonary reanimation, Biological parameters: haemoglobin, Platelets, lactates, Base excess, TP (sec and %), INR, PTT, Fibrinogen, Drugs use: Tranexamic acid (date/time), vasoactive, Vitamin K, Fibrinogen, Prothrombin complex concentrate, rFVIIa, Red blood cell (number in the first hour, date/hour of each Red blood cell), platelets units, fresh frozen plasma.
 
Imaging: type of imaging, results: positive or negative for free fluid, date/time of imaging.
 
Diagnosis: AIS final, ISS final, Medical past, use of anticoagulant/antiaggregant before trauma
 
Outcome: Date/time of death, Early death (<12 hours), Early death (<24 hours), number of red blood cell in 24 hours, Massive transfusion (defined as ≥ 10 red blood cells in the first 24 hours).
 
Depending of the availability of requested variables in the registry, we will ask for complementary variables.
 
Comparison:
 
Performance comparison of pre-existing scores (TASH, ABC and BATT scores) in term of overall performance, discrimination and calibration.
 
Evaluation of clinical utility and feasibility in prehospital settings and emergency admission.

Intervention:
	
Comparison of score performances (Overall performance, discrimination and calibration)

Control Intervention (if applicable):
	
No group controls

Number of Participants with Rationale:
	
The number of participants will depend of the Swiss Trauma Registry Database. We project to include 10'000 participants for our study. A post-hoc power calculation will be performed.


Study Duration:
	
11 months

Study Schedule:
	
From August 2020 to June 2021

Investigator(s):	
[name] Study Director Service des Urgences Centre hospitalier Universitaire Vaudois (CHUV) [name] [name] Email : [contact]
 
Doctor [name] Study Director Service des Urgences Centre hospitalier Universitaire Vaudois (CHUV) [name] [name] Email : [contact]
 
[name] Principal investigator Service des Urgences Centre hospitalier Universitaire Vaudois (CHUV) [name] [name] Email : [contact]

Study Centre(s):	
Multi-centre study including 12 Swiss Trauma Centre included in the Swiss Trauma Registry (Centre Hospitalier Universitaire Vaudois, Hôpitaux universitaire Genevois, Inselspital Bern, Universitätsspital Basel, Universitätsspital Zürich, Kantonsspital St. Gallen, Luzerner Kantonsspital, Kantonsspital Aarau, Kantonsspital Graubünden, Kantonsspital Winterthur, EOC – Ospedale Regionale di Lugano, Gesundheitsnetzwerk Wallis – Standort Sion)

Statistical Considerations:	
Comparison between scores:
 
 - Overall performance: Brier score - Discrimination: C-statistic, AUROC curve and calculation of likelihood ratio, sensitivity and specificity. - Calibration: Global calibration, calibration curve with intercept and slope calibration. 
Missing data: To estimate baseline risk for the full dataset, we will replace missing predictors using multiple imputation by chained equation.
 
Please referring to the Statistical Analysis Plan

GCP Statement:	
This study will be conducted in compliance with the protocol, the current version of the Declaration of Helsinki, the ICH-GCP or ISO EN 14155 (as far as applicable) as well as all national legal and regulatory requirements.

Study Procedure/Flowchart with Timelines: Study specific Examinations have to be clearly identified

1st step :Request database to the Swiss trauma registry, redacting the statistical analysis plan and study registration on Clinicaltrials.org (August-September 2020)

2nd step: Statistical Analysis (October 2020)

3rd step: Results (December 2020)

4th step: Publication

Storage of Data-and Samples for Future Research Aims: no**Ethical Considerations:**

1. Please describe the potential gain of new knowledge obtained with this study, and its meaning for patients/society.

Answer n°1:

Due to the study population (Swiss Trauma Registry) which is partly integrated into the German DGU-Register, we expect good transportability of the TASH score to the Swiss Trauma Registry in term of overall performance, discrimination and calibration. The ABC score should show lowers results in terms of discrimination due to his validation on small cohorts exclusively in north America. The new BATT score predicting death due to bleeding, has been validated on a large English Cohort of more than 100'000 patients. It identifies all patients with haemorrhage and not only patients who have received a massive transfusion subject to survival bias. In this context, the BATT score provides good discrimination with only simple physiological variables available on the trauma scene. In case of its external validation on the swiss trauma registry as part of our study, its feasibility would make its clinical utility superior to other pre-existing scores while identifying a greater number of patients requiring early management. Its application would activate a massive transfusion plan directly on the trauma scene and save precious time.

2. Please give an assessment of the benefit/risk relationship for the patient.
3. Please explain, why the methodology is also ethically appropriate to gain new generalizable knowledge (for ex. double-blind, placebo, sham, vulnerable subjects, emergency cases, partial information only etc.)

Answer n°2-3:

Due to the retrospective aspect of our observational study based on an anonymized register (identity, date of birth, trauma scene and hospital location unknown according to the swiss law: Art. 2 HRA), we don't identify any risk of being harmful to our population. In case of external validation of the scores, we identify benefits for the population in terms of trauma care. Without any risk for the patient, the potential gain of knowledge obtained with this study is high and will contribute to improve trauma care in respect of the fundamental principles of Medical ethics.

The most relevant References:

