5.2.2. Accuracy

The accuracy will be assessed using the Brier score:

$$\text{Brier Score} = \frac{1}{N} \sum_{i=1}^n (Y - p)^2$$

Where Y is the observed outcome and p is the prediction of the model

The Brier score depends on the prevalence of the outcome, the investigators will also calculate the scaled Brier score to account for the baseline risk of Massive transfusion:

$$\text{Scaled Brier score} = \frac{1 - \text{Brier}}{\text{Brier max}}$$

The scaled Brier score ranges from 0% to 100% and indicates the degree of error in prediction. A scaled Brier score of 0% shows perfect accuracy.

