5.2.3. Discrimination

Discrimination is the ability of the score to correctly identify patients with the outcome. The investigators will estimate the sensitivity, specificity, positive and negative likelihood ratio for the defined threshold of each score (ABC, TASH, BATT).

The likelihood ratio is the likelihood of a positive score in a patient with the outcome compared to the likelihood of a positive score in a patient without the outcome. The positive likelihood ratio is the ratio of sensitivity to 1-specificity. The negative likelihood ratio is the ratio of 1-sensitivity to specificity. A positive likelihood ratio of 10 or above will result in a large increase in the probability of the outcome. A negative likelihood ratio of 0.1 or less will result in a large decrease in the probability of the outcome.

The investigators will plot the Receiving Operating Characteristic (ROC) curve which is the sensitivity (true positives) on 1-specificity (false positives) for each defined threshold of each

score. An ideal score will reach the upper left corner (all true positive with no false positive). The investigators will estimate the area under the ROC curve (AUROC) that corresponds to the concordance statistic (C-Statistic) for binary outcome. A C-statistic of 1.0 shows perfect discrimination ability.

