5.2.4. Calibration

Calibration is the agreement between observed and predicted outcomes. The investigators will mostly estimate calibration as the difference between the mean predicted and observed probabilities and the ratio of the predicted and observed number of events (P/O). The investigators will plot the observed and predicted probabilities of massive transfusion by decile of the score and with local regression based on LOESS algorithm. The investigators will estimate the calibration intercept and slope of the calibration plot as a measure of spread between predicted and observed outcome. Ideally, the intercept would be zero indicating that the predictions are neither systematically too low or too high and the slope would be 1.

Unfortunately, the investigators cannot estimate the calibration of the BATT score, because of its different outcome (death due to bleeding and not the massive transfusion as the TASH and ABC score). For the BATT, calibration will be assessed with the outcome of death due to bleeding or early death.

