5.4 Statistical Software

All analyses will be performed using STATA software (version 16.0; Stata Corp, College Station, TX, USA).

6. Discussion

Due to the study population (STR), which is partly integrated into the German DGU-Register, the investigators expect good transportability of the TASH score to the Swiss Trauma Registry in terms of overall performance, discrimination and calibration. The ABC score should show lowers results in terms of discrimination due to its validation on small cohorts exclusively in North America. The new BATT score predicting death due to bleeding has been validated on a large English cohort of more than 100,000 patients. It identifies all patients with haemorrhage and not only patients who have received a massive transfusion subject to survival bias. In this context, the BATT score provides good discrimination with only simple physiological variables available at the trauma scene. In case of its external validation on the STR as part of our study, its feasibility would make its clinical utility superior to other pre-existing scores, while identifying a greater number of patients requiring early management. Its application would activate a massive transfusion plan directly at the trauma scene and save precious time.

7. Conclusion

This SAP presents the principles of analysis of the MTP study and discusses its major methodologic and statistical concerns. The investigators hope that the results of the MTP study will be as transparent and robust as possible, so that the investigators minimised the risk of outcome reporting bias and data-driven results.

8. Tables and Figures

Table 1. Overview of all variables requested from the STR for the MTP study.

Variable	Prehospital	In-hospital Trauma room	First 24 hours
Demographics			
Age	X		
Gender	X		
Type of accident	X		
Mechanism of Injury	X		
Accident date	X		
Accident time	X		
Medical past	X		
Arrival on scene (paramedics, date/time)	X		
Arrival on scene (medics, date/time)	X		
Physician Staffed Ambulance (yes/no)	X		
Hospital Arrival (date/time)		X	
Clinical examination (first measures recorded)			
Heart Rate	X	X	
Systolic blood pressure	X	X	
Respiratory rate	X	X	
Pulse oximetry	X	X	
Temperature	X	X	
Glasgow Coma Scale	X	X	
Cardiopulmonary Reanimation	X	X	
Biological parameters			
Haemoglobin		X	
Platelets		X	
Lactates		X	
TP		X	

INR		X	
PTT		X	
Fibrinogen		X	
Base excess		X	
Therapy			
Vasoactive drugs (doses, type)		X	
Tranexamic acid (doses, date/time)	X	X	

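### Clinical utility is promised, and a BATT advantage on it anticipated, but no planned analysis measures utility

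*Protocol*

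**What the plan says.** Under Measurements and procedures, the protocol synopsis gives two separate comparison items. One is performance (overall performance, discrimination, calibration). The other is "Evaluation of clinical utility and feasibility in prehospital settings and emergency admission".

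The measures planned to deliver these are:

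- Protocol, Statistical Considerations: Brier score, calibration, and "Discrimination: C-statistic, AUROC curve and calculation of likelihood ratio, sensitivity and specificity".
- SAP 5.2.2: "The accuracy will be assessed using the Brier score", with a scaled version.
- SAP 5.2.3: "The investigators will estimate the sensitivity, specificity, positive and negative likelihood ratio for the defined threshold of each score (ABC, TASH, BATT"), a ROC curve, and "The investigators will estimate the area under the ROC curve (AUROC) that corresponds to the concordance statistic (C-Statistic) for binary outcome".
- SAP 5.2.4: mean predicted against observed risk, the predicted-to-observed ratio, a LOESS plot, and "The investigators will estimate the calibration intercept and slope of the calibration plot". BATT is excluded from calibration against massive transfusion because it predicts death due to bleeding.

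The cut-offs are not stated in SAP 5.2.3. They can be inferred from the Table 2 bands (TASH 18-31, BATT 8-12, ABC 2-4), and Figure 2 confirms ABC at 2 points or more.

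SAP section 6 says that if BATT is externally validated, "its feasibility would make its clinical utility superior to other pre-existing scores". The protocol background, the protocol's ethical considerations and SAP 2.1 say much the same. All of them add that BATT would identify more patients who need early care.

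**The concern.** Utility is a promised result and a conclusion about it has been drafted, but no analysis leads from one to the other. Nothing planned sets a risk at which one would act, weighs a missed case against a false activation, or compares the scores at a common operating point. Nor is there any measure of feasibility.

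The number of patients a score identifies depends directly on its cut-off. Two scores read at unaligned cut-offs can differ in sensitivity, specificity and likelihood ratios for that reason alone. If the plan is followed as written, the study could report that BATT is more useful with no result that bears on the question. If a threshold range were chosen after the results were seen, the choice would be data-driven, which SAP section 7 says the plan is meant to avoid.

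**Working it through.** **1. Planned measures against the promise**

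| Planned measure | Available for all three scores on massive transfusion? | Weighs missed cases against false activations? |
|---|---|---|
| Brier, scaled Brier | Needs predicted risks; the SAP figures give them for TASH only | No |
| AUROC | Yes | No; it summarises all cut-offs |
| Sensitivity, specificity, LR+, LR- | Yes, at one cut-off per score | No; no weights are set |
| Calibration | Not for BATT (SAP 5.2.4); no ABC risks given | No |

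**2. Are the cut-offs aligned?** The maximum TASH points in Figure 1 sum to 8+4+4+2+3+6+3+1 = 31, which matches the top of the Table 2 band 18-31. Figure 1 gives a 50% risk at 18 points. A straight line through the logits of the Figure 1 risks for 9 to 23 points is logit p = -5.46 + 0.303 × TASH. It returns 50.0% at 18, with a largest deviation of 0.5 percentage points, so the table is consistent with itself. No risk is given for ABC 2 or BATT 8, and BATT's risk concerns another outcome. Alignment therefore cannot be shown from the documents.

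**3. Effect of the cut-off alone.** Take one marker with an assumed AUROC of 0.85 under a binormal model (separation √2 × z(0.85)):

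| Cut-off (SD above the non-event mean) | Sensitivity | Specificity | LR+ | LR- |
|---|---|---|---|---|
| 0.5 | 0.83 | 0.69 | 2.7 | 0.24 |
| 2.0 | 0.30 | 0.98 | 13.0 | 0.72 |

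The marker is the same in both rows.

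**4. Net benefit.** The documents give no sensitivity, specificity or prevalence, so all inputs here are assumed. With prevalence 5% and N = 10,000 there are 500 events and 9,500 non-events.

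- Rule A (sensitivity 0.35, specificity 0.98): TP = 0.35 × 500 = 175; FP = 0.02 × 9,500 = 190; LR+ = 0.35/0.02 = 17.5; LR- = 0.65/0.98 = 0.66.
- Rule B (0.75, 0.86): TP = 375; FP = 0.14 × 9,500 = 1,330; LR+ = 0.75/0.14 = 5.4; LR- = 0.25/0.86 = 0.29.

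Net benefit per 10,000 = TP - FP × pt/(1-pt), where pt is the risk at which one would act.

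| pt | Weight pt/(1-pt) | A | B | Act on all |
|---|---|---|---|---|
| 5% | 0.0526 | 175 - 10 = 165 | 375 - 70 = 305 | 500 - 500 = 0 |
| 10% | 0.1111 | 175 - 21 = 154 | 375 - 148 = 227 | 500 - 1,056 = -556 |
| 20% | 0.25 | 175 - 47.5 = 127.5 | 375 - 332.5 = 42.5 | 500 - 2,375 = -1,875 |

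**5. Where the preferred rule changes.** The two are equal when pt/(1-pt) = (difference in TP)/(difference in FP):

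- Prevalence 3%: (0.40 × 300)/(0.12 × 9,700) = 120/1,164 = 0.103, so pt = 9.3%.
- Prevalence 5%: 200/1,140 = 0.175, so pt = 14.9%.
- Prevalence 10%: 400/1,080 = 0.370, so pt = 27.0%.

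A second assumed pair (0.40, 0.97 against 0.75, 0.85) crosses at 8.3%, 13.3% and 24.5% for the same prevalences. The ranking depends on a threshold that the SAP does not set.

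**6. Feasibility.** SAP Table 1 marks all three scores as prehospital, yet haemoglobin, base excess and free fluid are requested for the trauma room only. TASH needs all three, and ABC needs the last. The share of patients who can be scored on scene is not a planned result.

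**The case against.** Several parts of the opposing case stand.

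- A reader might infer that the SAP offers nothing beyond sensitivity, specificity and likelihood ratios. It also plans Brier, ROC/AUROC and calibration. AUROC does not depend on a cut-off, and the ROC curve shows the trade-off between sensitivity and specificity.
- A reader might infer that the three cut-offs are known to sit at different risks, with TASH the strictest. Only TASH 18 has a documented risk. The supportable statement is that the cut-offs are not tied to a common risk or outcome.
- A reader might infer that the SAP's remark on an LR+ of 10 or more would select Rule A. That remark is interpretive and is paired with an LR- of 0.1 or less. Rule B has the better LR-, so the planned output would show a trade-off.
- A reader might infer that the planned results can never rank the scores. A score with both higher sensitivity and higher specificity is better at every threshold. Otherwise net benefit follows from planned quantities and the observed prevalence once a threshold is named.

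The authors also rest utility mainly on whether a score can be applied on scene, and their claim is conditional on validation. Net benefit does not measure on-scene availability or time gained. In addition, utility is absent from the protocol's objectives and from the SAP's stated objective, so removing the promise would also cure the mismatch.

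These points narrow the concern and shape the fix. They do not supply the missing measure: feasibility is not measured either, and a score that can be computed on scene is not thereby more useful.

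**Conclusion.** The concern holds in a limited form. Utility is promised and a BATT advantage is anticipated, but no planned analysis measures it. The planned results do not rank the scores on usefulness when one gains sensitivity and another specificity.

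The illustration shows that the gap can reverse a conclusion. B leads by 140 net true positives per 10,000 at a 5% threshold, and A leads by 85 at 20%. The crossover lies between 9.3% and 27.0% for prevalence from 3% to 10%. These sizes rest wholly on assumed inputs and do not predict how TASH, ABC or BATT will perform. That the cut-offs are TASH 18 and BATT 8 is itself an inference from Table 2.

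The planned performance results are unaffected. What would lack support is the utility conclusion, so the change is worth making but does not threaten the primary analysis.

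**What to change.** Before data receipt:

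1. State the three cut-offs in SAP 5.2.3.
2. Add to SAP 5.2 a net-benefit analysis for massive transfusion, TP/N - FP/N × pt/(1-pt), over a threshold range that the investigators choose and justify. Compare the three binary rules with act-on-all and act-on-none, in the same patients and at the same time point, with bootstrap intervals for the differences. The binary form needs no predicted risk for ABC or BATT.
3. Add a sensitivity analysis on death due to bleeding or the SAP's early-death proxy. SAP 4.4 accepts that some patients die before reaching 10 units. Under massive transfusion, such patients flagged by BATT can count as false positives, particularly if the first-hour transfusion count is unavailable.
4. Report feasibility separately, as the share of patients in whom each score can be computed on scene and at admission, counted before imputation.
5. Limit the utility conclusion to these results.

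The alternative is to remove the utility and feasibility item from the protocol and the superiority wording from both documents.

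The cost is a short SAP paragraph and some further analysis of data already requested. The harder part is that the investigators must commit to a threshold range.
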